## Background

Diabetes is a serious health concern and due to its rapidly increasing incidence, especially in children and adolescents, has been declared a global epidemic by the World Health Organization. It is taking a heavy toll on the US economy - US\$ 376 billion annually that will increase to US\$ 490 billion in 2030 [1-3]. Glycemic control in children and adolescents with diabetes is limited by poor patient compliance. In addition to failing to adhere to appropriate diet and pharmacologic therapy, children and adolescents with diabetes who do not monitor their blood glucose frequently and make adjustments based on those measurements, have poor glycemic control and are at risk for developing long-term complications. The frequent (> 4 times daily) monitoring of blood glucose is an essential component of diabetes management as maintenance of blood glucose near the physiologic range enables the diabetic child to lead a healthy life and avoid long-term complications from diabetes [4, 5].

Commercial blood glucose-monitoring devices (BGMDs) employ a cost-effective biosensor that can be mass-produced and responds rapidly to glucose detection. The BGMDs require an automated lancet device to prick the fingertip for blood sampling, which is painful [6]. The development of BGMDs in the past 2 decades has improved by reducing the amount of blood needed for measurement and reducing the size of the lancet. In the past decade, minimally invasive glucose sensors have been developed that utilize interstitial fluid to determine glucose concentration that correlates well with serum glucose [7, 8]. Despite these improvements, children with diabetes are still apprehensive with these devices and perceive them as painful. Avoidance or non-compliance with current BGMDs places diabetic children at increased risk for long-term complications [6]. The goal of this proposal is to develop microneedle patches as a new method for interstitial fluid collection and subsequent glucose measurement to reduce pain and apprehension in children and adolescents with diabetes.

Microneedles have been developed to create transport pathways for small drugs, macromolecules, and fluid flow in a painless manner. They range in length from 150 – 900  $\mu\text{m}$  and the microscopic length permits appropriate collection of interstitial fluid but limits the extension into the abundant nerve-ending region of the dermis, thereby minimizing pain [9-11]. We have collected interstitial fluid with subsequent glucose measurements using hollow, glass microneedles previously however, it required a two-step process [12]. Hollow, glass microneedles were applied to human skin and suction was required to withdraw the interstitial fluid from the needles. The study showed a strong correlation between glucose levels in interstitial fluid and blood but, the two-step process was time-consuming and cumbersome, making it difficult to translate it into a point-of-care system.

The American Diabetes Association (ADA) recommends that diabetics maintain their plasma glucose in a strict range to prevent long-term complications of diabetes [13]. Children with diabetes who fail to appropriately monitor their blood glucose are not aware of how to adjust their diet and/or pharmacotherapy to optimize their glycemic control. In this project, we propose to target collection of interstitial fluid for glucose measurement from the painless application of solid microneedles in children with diabetes. Because these microneedles and continuous indwelling sensors for interstitial fluid glucose monitoring are both FDA-approved, this is a well-established and accepted medium from which to sample and measure glucose [6, 8].

Needle anxiety prevents ideal glycemic control and up to 50% of children and adolescents fail to monitor their blood glucose consistently [7, 14]. Microneedle patches could eliminate needle anxiety and improve adherence to proper glucose monitoring. Studies show microneedles reduce injection pain [9, 10] and increase patient and clinician acceptance for other injected drugs [15]. We will investigate if microneedle patches can improve adherence and compliance with glucose monitoring in children and adolescents with diabetes.

We have recently developed a simple process, to independently extract interstitial fluid from skin. The microneedles are made from biocompatible polymers or metal. Inserting these microneedles creates on create holes in the skin. These pores are pathways to draw out interstitial fluid out of the skin. The collected fluid is used for analysis. In a future design, the glucose-sensing functionality can be integrated into the patch backing (e.g., integrate a glucose test strip into the patch backing) to create a simple, one-step method of glucose monitoring.

We have used our original glass microneedle design to collect interstitial fluid more than 100 times in rats and in six adult human subjects. We have used stainless steel microneedles for drug/vaccine delivery in hundreds of mice. Polymer microneedles also have been tested in extensive animal studies and there is an ongoing Phase 1 human clinical trial on influenza vaccination using these microneedles.. We have used placebo microneedles of various designs in a number of different studies involving nearly 1000 microneedle insertions in close to 150 human subjects. The process of insertion of the microneedles has been simple and painless.

Overall, there is a need to improve glucose monitoring to prevent the costly long-term complications of diabetes. Existing alternatives have limitations that restrict widespread uptake. This project will provide a first detailed assessment of microneedle patches as an option for improved efficacy and acceptance of glucose monitoring in children with diabetes. Current efforts to develop alternative glucose monitoring methods (e.g., interstitial glucose measurement) have had minimal clinical impact due to the apprehension and discomfort associated with insertion of either a glucose sensor or lancet that requires penetration through the epidermal layer [6]. As a novel approach designed to address the shortcomings of other glucose measuring methods, especially in children, we propose the application of microneedle patches for interstitial fluid collection and subsequent glucose concentration measurement to achieve two improvements: (i) improved safety as a bloodless method with less tissue trauma and (ii) higher acceptance among pediatric patients and clinicians due to the painless and non-threatening patch design.

## **Procedures**

A cohort of 15 children and adolescents with diabetes will be recruited for the study. We hypothesize that glucose concentration collected from interstitial fluid will correlate with both capillary blood glucose (collected from a lancet and measured with a BGMD) and venous glucose (collected from an intravenous

catheter). In this aim, we will measure glucose concentrations collected from children and adolescents with diabetes (type 1 or type 2).

Glucose measurements from all three methods (interstitial fluid - microneedle, capillary blood - lancet, and venous blood - intravenous catheter) will be made simultaneously from each subject every hour from 8:30 AM – 11:30 AM. Suction (up to 500 mmHg) may be applied after microneedle treatment at the skin site for up to 1 hour to withdraw fluid ( $\leq 500 \mu\text{l}$  [microliters]) from the skin. Measurements will be taken every hour for the study period. Subjects will arrive in the morning after an overnight fast and will eat or drink a breakfast during the study visit. Subjects will be asked about the pain and apprehension with each device.

Pain and apprehension will be determined with the use of the visual analog pain scale (VAS) and a questionnaire. Each subject will be asked to rate their apprehension prior to receiving each method for blood or interstitial fluid collection as well as the pain associated with each method immediately after collection. Each subject will receive each method of glucose monitoring simultaneously. Similar to a cross-over study, each subject's apprehension, pain, and glucose with each method will be compared using the paired t-test method. Sample size is determined based on the number of subjects needed to achieve statistically significant differences in pain based on the VAS. In order to detect a pain difference of 20 mm with a standard deviation of 20 at a power of 95% and an alpha of 0.05, 15 subjects will be recruited.

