### Expected Outcomes

In this study, we will develop microneedle patches for collection of interstitial fluid for subsequent measurement of glucose concentration in an effort to improve patient compliance and cost (Fig 1). Recent studies have shown that intradermal microneedle insertion is less painful and strongly preferred by patients receiving drug delivery through injections [13-15]. We hypothesize that interstitial fluid collection using microneedle patches can improve glycemic monitoring in being as effective as conventional methods and in a less painful manner, thereby improving patient compliance. The microneedle patches will be fabricated at the Global Center for Medical Innovation at the Georgia Institute of Technology. Prior to use in human subjects, the microneedle patches will be sterilized by an approved sterility center.

**Fig. 1. Microneedle patches for interstitial fluid glucose monitoring. Prototype patches are shown with green dye in the microneedles for visual enhancement (left). Application of microneedle patches to the skin is simple (center). High magnification images of microneedles (right).**

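### Correlation plus a paired t-test on glucose cannot show that the patch matches conventional methods; compare microneedle and lancet errors against venous glucose, which the trial already measures

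*Combined protocol and SAP*

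**What the plan says.** The Procedures section gives one glucose hypothesis: "We hypothesize that glucose concentration collected from interstitial fluid will correlate with both capillary blood glucose", and likewise with venous glucose. It states no coefficient, error limit or margin, and calls neither comparator the reference.

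The three samples are taken together: "interstitial fluid - microneedle, capillary blood - lancet, and venous blood - intravenous catheter) will be made simultaneously from each subject every hour". The window is given as "every hour from 8:30 AM – 11:30 AM", which I read as four rounds per child.

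The only analysis named is in the same section: "each subject's apprehension, pain, and glucose with each method will be compared using the paired t-test method". It does not say how the hourly rounds are combined within a child.

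The number of children was set on another endpoint: "Sample size is determined based on the number of subjects needed to achieve statistically significant differences in pain based on the VAS".

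The Expected Outcomes section then hypothesizes that "interstitial fluid collection using microneedle patches can improve glycemic monitoring in being as effective as conventional methods", with no criterion for that statement.

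**The concern.** Matching conventional methods is a statement about accuracy relative to the lancet. Neither planned glucose analysis measures that.

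- **Correlation** is unaffected by a constant offset or a change of scale. It also rises with the spread of glucose, which should be wide when children go from fasting to fed.
- **The paired t-test** looks only at the mean difference. Errors that cancel on average are invisible to it, and without a margin a non-significant result is not evidence of agreement.

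A patch with large random error could therefore meet the correlation hypothesis, show no significant mean difference, and be described as equivalent to the lancet. With no reference named, a discrepancy between patch and lancet also cannot be assigned to either device. The venous sample taken in each round could settle this, but the plan describes no comparison of the two devices' error sizes.

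**Working it through.** **The plan's own figure.** Pain difference 20 mm, SD 20 (taken as the SD of paired differences), two-sided alpha 0.05, n = 15. The noncentrality is (20/20) × √15 = 3.87, and the noncentral t distribution gives power of 94.9% against the stated 95%. So 15 is essentially reproduced, but for pain only.

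**Assumptions for glucose.** The documents give no glucose mean, SD or device error. I assume venous glucose V with mean 180 mg/dL and SD 60 (range 40 to 80), clipped to 60–400 in simulation, and 15 children × 4 rounds = 60 pairs. The 20% and 15% limits used below are yardsticks of mine.

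**Smallest significant r (two-sided 0.05).** r = t/√(n − 2 + t²), which gives 0.51 for 15 pairs and 0.25 for 60 pairs treated as independent.

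**Device A: reads 30% low, 5% noise.**
- r = 60/√(3600 + 0.05² × (180² + 60²)) = 60/√3690 = 0.99. The mean absolute relative difference is 30%.
- The mean difference is −0.3 × 180 = −54 mg/dL. The paired t-test is significant in 100% of simulated trials.
- A passes on correlation and is caught by the t-test.

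**Device B: unbiased, 20% random error.** r = SD/√(SD² + 0.2² × (180² + SD²)).

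| Assumed SD | Calculation | r |
|---|---|---|
| 40 | 40/√(1600 + 1360) | 0.74 |
| 60 | 60/√(3600 + 1440) | 0.85 |
| 80 | 80/√(6400 + 1552) | 0.90 |

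- Simulated trials, with clipping and small samples, average slightly lower: about 0.72 to 0.88. The correlation over 60 pairs is significant in at least 99.8% of them.
- The mean difference is zero, so the t-test rejects at about its nominal 5%.
- The share of readings more than 20% from venous is P(|Z| > 1) = 32%, whatever the SD. The mean absolute relative difference is 0.20 × √(2/π) = 16%.
- B passes both planned checks.

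**Devices C and D** (venous mean 180, between-child SD 50, within-child SD 35).
- C compresses readings toward the mean (slope 0.5, noise SD 20): r = 0.82, t-test significant in 6% of trials, only 55% of readings within 15% of venous.
- D is precise with a small offset (−8 mg/dL, noise SD 6): 96% of readings within 15%, yet the t-test is significant in 100%. Its noncentrality is 8/(6/√4) × √15 = 10.3.

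**Can 15 children support an error comparison?**
- With one difference per child, the 95% confidence half-width is 2.145/√15 = 0.55 SD for the mean difference and about 0.97 SD for each limit of agreement.
- For the difference in absolute relative difference, assume a lancet error of 7% and independent errors. The SD of an absolute normal error is 0.603 times its SD. For a 20% patch, the per-round SD is √(0.1206² + 0.0422²) = 0.128. Over 4 rounds and 15 children the half-width is 2.145 × 0.128/(2 × √15) = 3.5 percentage points.
- The true excess error is then 0.798 × (0.20 − 0.07) = 10 points. For a 10% patch the half-width is 2.0 points. Any child-specific bias would widen both.

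**The case against.** The strongest reply is that correlation is not the only glucose analysis. A reader might infer that a patch reading 30% low would pass unnoticed. The documents do not support this: the planned paired t-test would detect such a device essentially every time. That part of the reply stands, and the concern rests on random and compressed error instead.

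A reader might also infer that the protocol concludes the patch is equivalent. It does not. Expected Outcomes hypothesizes this, and no rule ties a correlation to a declaration. Nor does the text call the capillary value a truth. It lists two comparators, and the paired comparison of methods may well include lancet against venous. What is missing is a comparison of error sizes.

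Finally, this is a 15-child early study sized on pain, and correlation is a common first aim for a new sampling route. That is fair and limits the severity. It does not make correlation evidence for the broader hypothesis. Absolute relative difference is also one reasonable accuracy measure among several.

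**Conclusion.** The concern holds in this form: as written, the glucose analyses cannot support a statement that the patch is as effective as conventional methods. A device with no mean bias but with 32% of its readings more than 20% from venous would typically satisfy both checks. A precise device with an 8 mg/dL offset would fail one of them.

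The direction does not depend on the assumed glucose spread: the 32% is independent of it, and the t-test rejection rate stays near 5% for SDs of 40 to 80. The values of r do depend on it. The error sizes and the 15% and 20% limits are assumptions, not figures from the documents. The absence of an accuracy criterion is judged on the text available for review, from which some pages were removed. The pain comparison is unaffected. The change should be made but is not critical to the conduct of the trial.

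**What to change.** In Procedures:

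1. Name venous glucose as the reference.
2. For both the microneedle and the lancet, report error against venous: mean bias with limits of agreement that allow for repeated rounds, and absolute relative difference averaged over rounds within each child.
3. Report the within-child microneedle-minus-lancet difference in absolute relative difference, with its 95% confidence interval.
4. Keep correlation and the paired t-test on glucose as descriptive.

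In Expected Outcomes, rest any statement of matching conventional methods on that interval, judged against an excess-error margin that the sponsor states before analysis. If no margin is stated, or the interval does not exclude it, limit the claim to saying that interstitial glucose correlates with the other two measurements.

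The cost is some wording and one more table, since every value is already collected. The downside is that with 15 children the interval may be wide and the claim correspondingly more modest.

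### The only analysis named for glucose, a paired t-test, cannot show the correlation or agreement the study is after, and no rule says how several hourly readings per child enter it

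*Combined protocol and SAP*

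**What the plan says.** All of this is in the combined protocol and SAP.

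- **Schedule (Procedures).** Glucose readings by the three methods "will be made simultaneously from each subject every hour from 8:30 AM" to 11:30 AM, and the section repeats: "Measurements will be taken every hour for the study period". That is 4 rounds, or 3 if one end of the window is excluded. The count is not stated. Children arrive fasting and "will eat or drink a breakfast during the study visit".
- **Hypothesis (Procedures).** "We hypothesize that glucose concentration collected from interstitial fluid will correlate with both capillary blood glucose", and likewise with venous glucose.
- **Aim (Expected Outcomes).** The patch is expected to "improve glycemic monitoring in being as effective as conventional methods".
- **Analysis (Procedures).** Each child's apprehension, "pain, and glucose with each method will be compared using the paired t-test method". The design is likened to a cross-over study. No other method is named for glucose.
- **Sample size (Procedures).** "Sample size is determined based on the number of subjects needed to achieve statistically significant differences in pain based on the VAS": 20 mm, SD 20, 95% power, alpha 0.05, 15 subjects. Glucose has no power statement.

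**The concern.** There are two gaps, and the first is the more important.

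1. **The test does not match the question.** A paired t-test asks whether the mean difference between two methods is zero. Two methods can have the same mean and be uncorrelated, or be highly correlated with a large constant bias. Neither the correlation hypothesis nor the hope of equal effectiveness is answered by the named test. In a sample of 15, a non-significant result is weak evidence that the methods agree.
2. **The repeats have no rule.** The test assumes independent differences, which one pair per child satisfies. The schedule yields 3 or 4 pairs per child per contrast. Averaging the hours, testing each hour, choosing one hour or entering every pair would give different intervals and p-values from the same data, and the choice would be open after the data are seen. Breakfast falls within the visit, so the rounds are not plain replicates.

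**Working it through.** **The plan's own figure.** Inputs from Procedures: difference 20 mm, SD 20 (read as the SD of the within-child difference), two-sided alpha 0.05, n = 15. Non-central t with 14 df and non-centrality (20/20) × √15 = 3.87 gives power 94.9%. The stated 95% is reproduced (n = 16 gives 96.2%). The number 15 therefore fits one pain difference per child and is not in question.

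**What a non-significant glucose difference would mean.** Same test, n = 15, true difference of 0.5 SD of the child-level difference: non-centrality 0.5 × √15 = 1.94, power 43.8%. The chance of a non-significant result is 1 − 0.438 = 56%.

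**What hangs on the handling of repeats (illustration).** Assumptions: 15 children, k rounds, normal differences with variance 1, no true difference at any hour, and the same correlation (ICC) between any two rounds of a child's between-method difference. The documents give no ICC, so every value is assumed. With k = 4 there are 15 × 4 = 60 pairs. The pooled test uses the standard error SD/√60, while the true variance of the mean is (1 + 3 × ICC)/60. The pooled sum of squares is distributed as (1 + (k−1)ICC)·χ²(14) + (1 − ICC)·χ²(15(k−1)), independently of the mean. Averaging the rejection probability over draws gives:

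| ICC | Type I error, 60 pairs pooled | Type I error, 45 pairs pooled (3 rounds) | Correct interval width ÷ pooled width (4 rounds) |
|---|---|---|---|
| 0 | 5.0% | 5.0% | 1.07 |
| 0.1 | 8.5% | 7.3% | 1.22 |
| 0.3 | 15.6% | 12.2% | 1.48 |
| 0.5 | 22.0% | 16.9% | 1.70 |
| 0.9 | 32.4% | 25.5% | 2.06 |

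The last column is t(14) × √((1 + 3 × ICC)/60) divided by t(59)/√60. At ICC 0.9 this is 0.533/0.258 = 2.06. At ICC −0.1 the pooled error is 2.0%, so inflation needs a positive ICC.

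Under the same assumptions, one mean difference per child holds 5% at every ICC. Four unadjusted hourly tests give a chance of at least one false positive of 18.5% at ICC 0, falling to 9.6% at ICC 0.9.

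**A limit of the child mean.** With assumed differences of +1, +1, −1 and −1 SD over the four hours, the child-mean test rejects only about 5% of the time, while Bonferroni-adjusted hourly tests reject over 99%.

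**Correlation.** Assume bivariate normal readings with a true r of 0.7 or 0.9, the same between and within children, and no time trend. The 95% interval from 60 pooled points then covers the true value 95%, 92%, 86% and 69% of the time at an ICC of the readings of 0, 0.3, 0.5 and 0.9.

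A repeated-measures correlation (within-child variation only) holds 95% in that setting, but not when both methods share a time trend. With an assumed common shift of 0, 0.5, 1 and 0.5 SD over the four rounds and r = 0.7, its median estimate rises to 0.76, 0.78 and 0.89, and its coverage of 0.7 falls to about 86%, 79% and 2%, at ICC 0.3, 0.5 and 0.9. A meal during the visit makes such a trend plausible, so this method is not a remedy in itself.

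**The case against.** **The plan does not say it will pool.** It speaks of each subject's values, likens the design to a cross-over study, and sizes the trial at one difference per child. The natural reading is 15 pairs. This stands. A reader might infer from the inflated error rates that the plan's glucose test runs at 8.5% to 32.4%. The documents do not support that: no pooling is announced and no ICC is given. Taken alone, the missing rule for repeats is missing detail. Reading the child as the unit still does not say how several readings become one value, and it supplies no method for correlation.

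**The direction of harm is easily misread.** A reader might suppose that pooling would flatter the microneedle. In the t-test it would do the opposite, because a false positive declares the patch different from the reference. In a correlation, pooling makes the interval too narrow whether the correlation is good or poor.

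**The plan does not say that non-significance will be taken as equivalence.** This is correct: equal effectiveness appears as an expected outcome, not as a decision rule. But no analysis is named that could support that outcome, so the inference is left open.

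**Glucose has no power claim in this small cohort sized on pain, and the choice of within-child summary is partly preference.** This is fair, and it limits the weight of the point. It does not remove the mismatch between the test and the hypothesis.

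**Conclusion.** The point holds as a mismatch of analysis and question. Followed exactly, the plan would test mean differences in glucose and would not answer its own hypothesis of correlation or its hope of equal effectiveness. The 56% chance of missing a 0.5 SD difference rests only on n = 15 and a two-sided 5% paired t-test.

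The missing rule for hourly repeats is a secondary gap. Its error rates are illustrative: they assume pooling, which is not planned, 4 rounds (or 3), exchangeable rounds and a positive ICC that the documents do not supply. The sample size of 15 is sound for the pain comparison under its stated inputs. Some pages of the document were not available, so the conclusion is confined to the text that was. The change should be made, and it concerns wording only.

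**What to change.** 1. Make the main glucose comparison an agreement analysis of microneedle versus venous and microneedle versus capillary glucose: bias with a 95% interval, and limits of agreement for repeated pairs, with the child as the cluster.
2. If the paired t-test is kept, apply it to each child's mean between-method difference over rounds in which both methods gave a value (15 differences, 14 df). Show the differences by hour as well, because fasting and post-breakfast differences of opposite sign could cancel in the mean.
3. If a correlation is reported, compute its interval with the child as the cluster, and say whether association driven by the shared meal response is part of the target. If repeated-measures correlation is chosen, state that it uses only within-child variation and that a shared time trend moves it away from the underlying correlation.
4. State that a non-significant difference will not be read as equivalence.

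**Cost.** Analysis wording only, with no extra children or samples. Intervals will be wider than pooling would give, by about 1.1 to 2.1 times at ICC 0 to 0.9 with 4 rounds. A child mean can hide opposite-signed hourly differences, which is why the by-hour display is needed.

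### All glucose comparisons pool one fasting-to-breakfast morning, so a statement that the patch matches conventional methods should be checked by glucose level and limited to the range observed (cheap improvement)

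*Combined protocol and SAP*

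**What the plan says.** Procedures sets the size of the study ("A cohort of 15 children and adolescents with diabetes will be recruited for the study") and one sampling window, in which readings by all three methods "will be made simultaneously from each subject every hour from 8:30 AM – 11:30 AM". The conditions are a fast followed by a meal: "Subjects will arrive in the morning after an overnight fast and will eat or drink a breakfast during the study visit". Either type of diabetes is eligible, and the available text describes no selection or timing rule intended to spread glucose values.

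Two statements govern the glucose analysis, both in Procedures. The hypothesis is one of correlation: "We hypothesize that glucose concentration collected from interstitial fluid will correlate with both capillary blood glucose", and likewise with venous glucose. The analysis is a paired comparison: "each subject's apprehension, pain, and glucose with each method will be compared using the paired t-test method". Neither is broken down by glucose level. The sample size rests on pain alone.

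Expected Outcomes goes further. It hypothesises that the patches "can improve glycemic monitoring in being as effective as conventional methods and in a less painful manner". No glucose range, margin or decision rule goes with that statement.

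**The concern.** A mean difference and a correlation taken over all readings mostly reflect where the readings lie. After breakfast these may be mainly in the middle and upper range. A patch that reads correctly there but too high when glucose is low shifts the overall mean difference only in proportion to the share of low readings. It also has little effect on a correlation driven by the total spread of glucose. Both summaries could therefore look satisfactory while a range that matters for monitoring was barely tested.

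At stake is how far the glucose result can be generalised. Nothing in the available text limits the effectiveness hypothesis to the levels sampled, so the plan followed as written could appear to support a broader statement than its data can bear.

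**Working it through.** **1. The plan's own sample-size figure.** Inputs from Procedures: pain difference 20 mm, SD 20 (taken as the SD of paired differences), alpha 0.05 (taken as two-sided), n = 15. The noncentrality is √15 × 20/20 = 3.87 on 14 degrees of freedom, which gives power 94.9%. The stated 15 for 95% power therefore reproduces. It says nothing about glucose coverage.

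**2. Amount of glucose data.** Rounds at 8:30, 9:30, 10:30 and 11:30 give 15 × 4 = 60 sets (15 × 3 = 45 if one end of the window is not sampled). Up to four sets come from the same child and are correlated.

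**3. Expected low readings.** The documents give no share p of low readings, so p is an assumption. The expected count is 60p. The chance of no low reading is (1 − p)^60 if readings are independent. A beta-binomial model with within-child correlation 0.5 allows for clustering.

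| Assumed p | Expected low readings of 60 | P(none), independent | P(none), correlation 0.5 |
|---|---|---|---|
| 1% | 0.6 | 55% | 73% |
| 2% | 1.2 | 30% | 53% |
| 5% | 3.0 | 5% | 20% |
| 10% | 6.0 | 0.2% | 4% |

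With within-child correlation 0.3 to 0.5, these readings come from about 0.3 to 3.6 children.

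**4. What a few agreeing readings can show.** If all k low readings agree, the one-sided 95% upper bound on the failure rate is 1 − 0.05^(1/k). For k = 3 it is 63%; for k = 10 it is 26%. This treats readings as independent and presumes an agree/disagree criterion that the plan does not define, so it is only an illustration.

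**5. Dilution.** An over-reading of 30 mg/dL confined to low readings moves the overall mean by 30 × (low readings)/60. That is 1.5 mg/dL with 3 low readings and 3 mg/dL with 6.

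**6. Simulation of the pooled summaries.** All inputs are assumptions. There are 15 children and four rounds, with 8% error on the patch reading and the patch 30 mg/dL too high whenever glucose is below 80 mg/dL. The t-test is on child means. The value 80 only places the assumed fault; it is not a proposed cut-off. Ranges show the spread between repeated runs.

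| Child mean / SD (mg/dL) | Within-child SD | Shifts by round | Low readings of 60 | r | t-test rejects |
|---|---|---|---|---|---|
| 150 / 40 | 20 | 0/40/50/20 | 1.4 | 0.95 | 5% |
| 130 / 40 | 20 | 0/40/50/20 | 3.4 | 0.95 | 10–11% |
| 150 / 60 | 20 | 0/40/50/20 | 4.2 | 0.96 | 10–12% |
| 110 / 30 | 20 | 0/40/50/20 | 4.9 | 0.94 | 18–20% |
| 120 / 40 | 20 | 0/40/50/20 | 5.0 | 0.95 | 16% |
| 120 / 50 | 25 | 0/40/50/20 | 7.6 | 0.96 | 25–27% |
| 110 / 40 | 25 | 0/30/20/0 | 11.5 | 0.94 | 51–53% |

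The t-test misses the fault in about 47% (100 − 53) to 95% (100 − 5) of trials. In the first five rows, where low readings are at most 5.0/60 = 8%, it misses it in at least 80%. The last row has 11.5/60 = 19% low readings, well above the 1% to 10% range in step 3.

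**The case against.** The strongest reply is that no conclusion of equal effectiveness is planned. Expected Outcomes states a hypothesis, without a success criterion. The glucose hypothesis in Procedures is only correlation, and the Background presents the work as a first assessment, leaving integrated sensing to a later design. Nothing available claims accuracy at low glucose. This stands: a reader might infer that the trial will declare unrestricted equivalence, but the documents do not say so. What remains is that nothing written holds a later statement to the range sampled.

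Second, the size of the problem is assumed throughout. This also stands. A reader might infer that low readings will be almost absent, or that a low-glucose fault would be undetectable. Neither follows from the documents: an overnight fast may produce some low values, and with enough of them the t-test finds the assumed fault about half the time.

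Third, a reader might infer that no agreement statistic could help. That is too strong. A plot of differences against glucose level would show both the range covered and any departure at its lower end. No such plot is in the plan.

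Fourth, a table by band may simply return no conclusion for low glucose. That is true, but it would be an accurate report of what was tested. Finally, some pages were not available, so statements about what is absent refer to the available text.

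**Conclusion.** The point holds as a cheap improvement, not as a defect that undermines the study. From the documents alone, glucose is observed in at most 60 correlated sets from 15 children on one fasting-to-breakfast morning. The stated comparisons pool all levels, and the effectiveness hypothesis has no range limit. How much this matters depends on assumptions. With 1% to 10% of readings low, 0.6 to 6 are expected. For the assumed 30 mg/dL fault below 80 mg/dL, the pooled t-test rejects in about 5% to 53% of trials over the glucose distributions tried, with r about 0.95 throughout. Often missed is therefore a fair description. There is no evidence in the documents that the patch has such a fault; the point is that the stated analysis could easily fail to show one.

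**What to change.** In Procedures, add an analysis of the microneedle-minus-venous difference by venous glucose level, with two parts:

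- a plot of the difference against venous glucose, with readings identified by child;
- a table giving the number of pairs, number of children, mean difference and spread in low, target and high venous bands, with cut-offs fixed before analysis.

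Intervals should allow for repeated readings within a child, for example through a child-level random effect.

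In Expected Outcomes, add that any statement on glucose effectiveness applies only to the venous range observed, and that none will be made for a band below a pre-set minimum number of pairs and of children. Both minima are needed, because up to four pairs come from each child: 10 pairs could come from three children. The sponsor should choose the cut-offs and minima before the data are seen.

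The cost is one plot, one table and a sentence or two of wording. No visit, sample or child is added, and no change to the visit or to clinical management is proposed. The downside is a narrower claim, possibly with no conclusion for low glucose.
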